8.3. Variables

8.3.1. Baseline Variables

Baseline variables are collected at index date. These variables reflect the patient's demographics and status at the initiation of filgotinib treatment including relevant medical history at or prior to the index date. Age (or date of birth), sex, disease duration and DAS28 are recorded at baseline for all registries.

Risk factors for MACE, VTE, and Serious and Opportunistic Infections

Variables will be collected at baseline to define the risk of each of the 3 outcomes of concern: MACE, VTE, and serious and opportunistic infections (see definitions in Section 6.1 and Annex 4).

The set of risk factor definitions were derived utilizing broader representation than that solely included in the RMP and then checked against data availability in each registry. The set of risk factors are provided in tables in each of the registry-specific sections, which reflect the availability of variables for each registry.

For MACE, the UK's Q-Risk score was used as a guide (Hippisley-Cox et al., 2008). We note that RA is a risk factor for MACE/CVD implying that the indicated patient population are at higher risk than the general population (after adjusting for age and sex). RA is available in all registries as a risk factor, as all patients have RA.

For VTE, the Jyseleca RMP mentions the following risk factors for VTE: "*prior history of VTE, advanced age, hormone replacement treatment, obesity, smoking, cancer or immobilization*". These risk factors are supplemented by considering the Caprini Score (Bahl et al., 2010), a perioperative assessment tool for new VTE. The Caprini Score highlighted the importance of a lack of mobility and hospitalization have on VTE risk.

For serious and opportunistic infections, the RMP highlighted that patients with RA were at increased risk and that the "*The reasons are multifactorial, including a poorly functioning immune system and concomitant use of immunosuppressant medications such as glucocorticoids*". The use of immunomodulators implies that patients initiating filgotinib are already at increased levels of risk. The set of risk factors for infection were supplemented by those indicated by the Rheumatoid Arthritis Observation of Biologic Therapy (RABBIT) Risk Score for serious infections (Zink et al., 2014).

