The Swedish Patient Register collects information on all hospitalized (inpatient-treated) patients, and all visits to nonprimary outpatient care (such as a visit to a rheumatologist). Diagnoses are assigned by the treating/discharging physician, as well as date of discharge, discharging hospital, and department. Diagnoses are coded according to the International Statistical Classification of Diseases and Related Health Problems (ICD), with Version 8 used until 1986, Version 9 from 1987 to 1996, and Version 10 since 1997. The inpatient component was originally initiated by several counties in 1964, had 85% countrywide coverage in 1983, and is considered complete since 1987. Validation against medical files have found an overall error rate in the main diagnoses of 4% at the ICD chapter level, and 12% at the 3-digit level. The outpatient component of the Swedish Patient Register was initiated with nationwide coverage in 2001. Overall, 13% of outpatient visits lack records, but coverage is higher for somatic public care (including most rheumatology care). Chart reviews and validation of the RA diagnosis based on different algorithms applied to the register data indicate a positive predictive value for a register-based diagnosis of RA around 90% (S. Eriksson et al., 2013; Knight et al., 2008).

C) The Swedish Cancer Register

The Swedish Cancer Register was established in 1958 and contains information on date of cancer (and some selected precancers) onset, and type of cancer according to the ICD classification and morphology/histology. Approximately 99% of cancers have been morphologically verified. Reporting of incident cancers (including invasive malignancies as well as cancer in situ) is mandatory and semiautomated, resulting in an estimated coverage greater than 95% (Barlow et al., 2009; Mattsson & Wallgren, 1984).

D) The Medical Birth Register

The Medical Birth Register contains prospectively provided data from antenatal, obstetric, and neonatal records since 1973, and covers all live and still births (but not all miscarriages) in Sweden. Among the variables covered are maternal age, parity, smoking and family situation in early pregnancy, and the infant's birth weight and length, gestational age (primarily based on ultrasound dating), and Apgar score. Complications and mother's and infant's morbidities are coded according to the ICD, with Version 8 used until 1986, Version 9 from 1987 to 1996, and Version 10 since 1997.

E) The Cause of Death Register

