ANNEX 4. DEFINITION OF BASELINE DISEASES IN ARTIS, BIOBADASER, BSRBR-RA, DANBIO, AND RABBIT

The following medical code-lists were created for the long-term safety PASS (GS-EU-417-9047) and were reviewed by the registries.

	BSRBR-RA, RABBIT, BIOBADASER	ARTIS, DANBIO
Safety Risk	Operationalization (final list to be defined based on reported endpoints in each register)	Operationalization
Serious and opportunistic infections	Hospitalization and/or use of parenteral antibiotics + MedDRA Infections and Infestations SOC 10021881.	Hospitalizations in the Patient Register listing as main diagnosis ICD10codes below. If main diagnosis is RA, contributory diagnoses are also considered. A00B99 (excluding A33 and A50), D73.3, E32.1, G00G02, G04.2, G05G07, H00.0, H44.0, H60.0H60.3, H66H67, H70, I30.1, I40.0, J00J22, J32, J34.0, J36, J39.0J39.1, J44.0, J85, J86, K04.4, K04.6, K04.7, K10.2, K11.3, K12.2, K14.0, K57.0, K57.2, K57.4, K57.8, K61, K63.0, K65.0, K65.1, K65.2, K65.9, L00L08, L30.3, M00M01, M46.2M46.5, M60.0, M65.0, M71.0, M71.1, M72.6, M86, N13.6, N15.1, N15.9, N30.0, N30.8, N34.0, N41.2, N43.1, N45.2, N45.3, N45.4, N48.2, N61, N70, N73, N75.1.
Herpes zoster/ Varicella zoster	10019974 Herpes zoster, 10019983 Herpes zoster ophthalmic, 10030865 Ophthalmic herpes zoster, 10058428 Herpes zoster multidermatomal, 10063491 Herpes zoster oticus, 10065038 Herpes zoster disseminated, 10065119 Necrotising herpetic retinopathy, 10072210 Genital herpes zoster, 10074241 Varicella zoster gastritis, 10074245 Herpes zoster pharyngitis, 10074248 Herpes zoster meningoencephalitis, 10074253 Herpes zoster necrotising retinopathy, 10074254 Varicella zoster pneumonia, 10074254 Varicella zoster pneumonia, 10074259 Herpes zoster meningitis, 10074297 Herpes zoster cutaneous disseminated.	Hospitalizations in the Patient Register listing as main diagnosis ICD10codes A02, A15A19, A31, A32, A43, A48.1, B02, B38, B39, B40, B44, B45, B58, B59. If main diagnosis is RA, contributory diagnoses are also considered.
Malignancy	Malignant or unspecified tumours.	All invasive malignancies recorded in the cancer register, excluding NMSC.

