	
Intraventricular haemorrhage; 10022841 Intraventricular haemorrhage neonatal; 10024119 Left ventricular failure; 10024242 Leriche syndrome; 10034476 Pericardial haemorrhage; 10036511 Precerebral artery occlusion; 10039163 Right ventricular failure; 10039330 Ruptured cerebral aneurysm; 10042316 Subarachnoid haemorrhage; 10042434 Sudden death; 10047279 Ventricle rupture; 10048380 Aneurysm ruptured; 10048761 Atrial rupture; 10049418 Sudden cardiac death; 10049993 Cardiac death; 10050403 Carotid artery dissection; 10051093 Cardiopulmonary failure; 10051328 Carotid aneurysm rupture; 10052019 Femoral artery occlusion; 10053633 Cerebellar artery occlusion; 10053649 Vascular rupture; 10053949 Vascular pseudoaneurysm ruptured; 10055803 Haemorrhage coronary artery; 10058178 Aortic occlusion; 10060874 Aortic rupture; 10060953 Ventricular failure; 10060964 Arterial haemorrhage; 10062585 Peripheral arterial occlusive disease; 10062599 Arterial occlusive disease; 10063081 Acute left ventricular failure; 10063082 Acute right ventricular failure ; 10063083 Chronic left ventricular failure; 10063084 Chronic right ventricular failure; 10064595 Haemorrhagic arteriovenous malformation; 10064601 Iliac artery occlusion; 10065441 Venous haemorrhage; 10065558 Aortic arteriosclerosis; 10067057 Basal ganglia haemorrhage; 10067116 Carotid arteriosclerosis; 10068119 Aortic dissection rupture; 10068119 Aortic dissection rupture; 10068230 Cardiorenal syndrome; 10069694 Brachiocephalic artery occlusion; 10069695 Subclavian artery occlusion; 10069696 Coeliac artery occlusion; 10071716 Vertebral artery dissection; 10072043 Central nervous system haemorrhage; 10072789 Iliac artery rupture; 10073565 Intracranial artery dissection; 10073565 Intracranial artery dissection; 10073681 Epidural haemorrhage; 10075449 Brachiocephalic arteriosclerosis; 10076203 Radiation associated cardiac failure.
	

Venous thromboembolism (deep venous thrombosis and pulmonary embolism)
	
10037377 Pulmonary embolism; 10051055 Deep vein thrombosis; 10061408 Venous thrombosis limb; 10063909 Post procedural pulmonary embolism; 10066881 Deep vein thrombosis postoperative.
	
Main diagnosis in the Patient Register, in or outpatient component, of the following ICD10 codes: I26.9, I26.0, I80.1, I80.2, I80.3, I80.8, I80.9, I81.0, I82.0, I82.1, I82.2, I82.3, I82.8, I82.9. Or, pulmonary embolism I26.0 listed as the underlying cause of death.

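### Annex 4 gives only ICD-10 codes for the ARTIS history of VTE, cardiovascular disease and serious infection, so an admission before 1997 cannot be matched although the history window is open-ended

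*Protocol*

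**What the plan says.** **Window.** Protocol Section 8.3.1 describes baseline variables as "including relevant medical history at or prior to the index date". No look-back limit is given. For the three outcomes of concern it points to the definitions: "MACE, VTE, and serious and opportunistic infections (see definitions in Section 6.1 and Annex 4". Table 3 lists history of cardiovascular disease, history of VTE and previous serious infection as available in ARTIS.

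**Source.** Section 8.4.1 states that Patient Register diagnoses are coded in ICD "with Version 8 used until 1986, Version 9 from 1987 to 1996, and Version 10 since 1997". On coverage it says: "The inpatient component was originally initiated by several counties in 1964, had 85% countrywide coverage in 1983, and is considered complete since 1987". The outpatient part came later: "The outpatient component of the Swedish Patient Register was initiated with nationwide coverage in 2001".

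**Codes.** In the ARTIS/DANBIO column of Annex 4, serious infection is defined as "Hospitalizations in the Patient Register listing as main diagnosis ICD10codes below" and VTE as "Main diagnosis in the Patient Register, in or outpatient component, of the following ICD10 codes". The MACE entry uses I20.0, I21 and I60–I64, plus I00–I99 as main cause of death. In the table of other medical history, the only code column is headed ICD10; it covers infection, renal impairment, diabetes and myocardial infarction. The annex gives no ICD-8 or ICD-9 equivalents for these items, no mapping rule and no 1997 start date.

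**The concern.** Three statements do not fit together: an unlimited history window, a register whose diagnoses before 1997 are in ICD-8 or ICD-9, and code lists that read only ICD-10. Annex 4 says its lists were made for the long-term safety study. There they would serve events during follow-up, all of which fall in the ICD-10 period. Here they are reused under a heading about baseline diseases.

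The items exposed are one-off events. A VTE, infarction, stroke or serious infection that led to a single admission before 1997 need not be coded again. The error is one-directional, because a missing code can only turn a history into no history. It bears on the first-listed objective in Section 7, the proportion of users at high risk at baseline. Prior VTE is the first VTE risk factor that Section 8.3.1 quotes from the risk management plan.

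**Working it through.** **Step 1: set the periods side by side.**

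| Period | Inpatient records (8.4.1) | Outpatient records (8.4.1) | ICD version | Matched by the Annex 4 lists? |
|---|---|---|---|---|
| 1964–1986 | partial; 85% coverage in 1983 | none | 8 | no |
| 1987–1996 | complete | none | 9 | no |
| 1997–2000 | complete | none | 10 | yes |
| 2001 on | complete | nationwide | 10 | yes |

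Ten years of complete inpatient data, 1987–1996, are held but not matched, plus earlier partial years. The gap concerns inpatient diagnoses only.

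**Step 2: which items are affected.** VTE, MACE, myocardial infarction and serious infection are affected. Diabetes and renal impairment also have ICD-10 codes only, but they are chronic and likely to be coded again after 1997. Malignancy and skin cancer come from the Cancer Register (skin cancer with ICD-O/2 and ICD-7 codes), joint prosthesis from operation codes, and hyperlipidemia from drug treatment. These do not depend on the Patient Register's ICD version.

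**Step 3: how far back.** Table 2 plans data collection in the last registry from Q2 2022 to Q2 2026. A missed event therefore lies at least about 2022 − 1997 = 25 to 2026 − 1997 = 29 years before index. A patient aged 50 at index was 20–24 in 1996; one aged 75 was 45–49.

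**Step 4: illustrative share of events before 1997.** The documents give no such share. Assumptions:
- index year 2024;
- first-event incidence proportional to g^(age/10) from age 18, with g between 1.3 and 2.0;
- every event hospitalized;
- no later re-coding and no mortality.

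For age a at index, the share before 1997 is

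s = [g^((a−27)/10) − g^1.8] / [g^(a/10) − g^1.8].

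- Age 50 (Section 8.2.1 gives a mean of about 50 for all biologic starters in ARTIS, not filgotinib users):
 - g = 1.3: (1.828 − 1.604)/(3.713 − 1.604) = 10.7%;
 - g = 2.0: (4.925 − 3.482)/(32 − 3.482) = 5.1%.
- Age 55: 8.3–18.3%.
- Age 75: 13.7–34.6%.

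At age 50 the whole share falls in 1987–1996, because such a patient reached 18 in 1992. At age 75 the part in 1987–1996 is 7.8–14.6%.

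**Step 5: effect on a history proportion.** Observed = P(1 − s). The protocol's own precision example gives the scale: P = 10%, n = 300, SE = √(0.10 × 0.90/300) = 1.73%, 95% CI 6.6% to 13.4%, as Section 8.5 states.

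| Assumed true P | Loss at age 50 (s = 5.1–10.7%) | SE at n = 300 | Loss in SE |
|---|---|---|---|
| 5% | 0.25–0.53 points | 1.26% | 0.20–0.42 |
| 10% | 0.51–1.07 points | 1.73% | 0.29–0.62 |

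At age 75 and P = 5% the loss is 0.69–1.73 points, or 0.55–1.37 SE. The values of P are assumed. These figures concern a single history item, not the high-risk proportion.

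**The case against.** **The statistical analysis plan may settle it.** Section 8.7 leaves detailed methods to that plan, which is not shown, and code mapping could be set there. A reader might infer that the protocol rules patients with pre-1997 events to be without history. It states no such rule; this follows only from applying the lists as printed. What remains is that the protocol itself fixes lists that cannot read part of the window it sets.

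**The lists may not be the full history algorithm.** Annex 4 has no list labelled history of cardiovascular disease, and its table of other medical history has no row for VTE or stroke. That is fair, but Section 8.3.1 refers to Annex 4 for the baseline definitions, and every Patient Register diagnosis list there is ICD-10.

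**The effect is small.** Re-coding after 1997, mortality after early infarction or stroke, and events never hospitalized all shrink the loss. Table 3 lists many other VTE factors, such as age, smoking, cancer and surgery, so a missed history changes the high-risk result only where no other factor already classifies the patient. This stands. A reader might take the figures for ages 55–75, about 8–35% of past events, as the size of the problem. Those ages are assumed; the one ARTIS age in the protocol gives 5–11%, and both are upper-end figures for the reasons just given.

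**Comparison with other registries.** A reader might infer that the Swedish proportion is biased downward relative to the registries that collect history on forms. The documents do not support that. Table 8 lists neither history of VTE nor previous serious infection for RABBIT. Table 6 marks previous serious infection as only partly available in BSRBR-RA. Section 8.9 concedes that medical history may rely on memory. No contrast between registries is planned.

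**DANBIO.** It shares the Annex 4 column, and its hospital register starts in 1976. However, Section 8.4.4 describes its diagnoses as ICD-10 and gives no changeover date, so the same gap cannot be asserted there.

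**Conclusion.** The mismatch is real and visible in the protocol alone. For ARTIS diagnoses taken from the Patient Register, the ICD-10 lists cover only 1997 onward, while the stated window has no start and inpatient data are complete from 1987. Used as printed, the lists under-ascertain history of VTE, infarction, stroke and other cardiovascular disease, and serious infection. A patient whose only record precedes 1997 would count as having no history.

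The bias in these items is downward, and the high-risk proportion may be biased the same way. It is probably small. The illustration gives about 5–11% of past first events at age 50, or 0.25–0.53 points if 5% truly have the history, and more in older patients. It rests on an assumed index year, incidence pattern and prevalence, and ignores re-coding and mortality. The documents do not allow the actual size to be measured. The loss does not shrink as the sample grows, and it is cheap to remove.

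**What to change.** In Annex 4, add ICD-9 and, where usable, ICD-8 equivalents for the one-off ARTIS history items: VTE, infarction, stroke and other cardiovascular disease, and serious infection. Read inpatient history from 1987 and state that year as the ARTIS look-back. Diabetes and renal impairment can stay as they are.

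If the mapping is not done, state in Section 8.3.1 or Annex 4 that ARTIS history from the Patient Register starts in 1997, and list the resulting under-ascertainment in Section 8.9. That also removes the contradiction, though it does not recover the events.

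For DANBIO, only check whether earlier ICD versions apply to its hospital register and, if so, treat it in the same way.

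The cost is a code-mapping table and some programming on data that ARTIS already links. No new data collection is needed.

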8.4.2. BIOBADASER

This study will be conducted by making secondary use of data collected by BIOBADASER. BIOBADASER collects baseline data from the recruiting clinician or directly from each patient enrolled in the registry using an electronic standardized form. Information for this study is recorded by BIOBADASER at (1) baseline as a part of the patient's routine consultations, and (2) during follow-up as a part of the patient's routine consultation used for the control of the disease or at least once a year (follow-up visit).

This study will be conducted by making secondary use of data collected by BIOBADASER. BIOBADASER collects baseline data from the recruiting clinician or directly from each patient enrolled in the registry using an electronic standardized form. Information is recorded by BIOBADASER (1) at baseline; (2) when an AE or change in treatment occurred (biologic therapy or with synthetic molecules with an identifiable target), for any other reason during this time period; and (3) as a part of the patient's routine consultation used for the control of the disease or at least once a year (follow-up visit). Data are also recorded when death occurs for any reason and, in the case of discontinuation of treatment, due to remission or other causes.

8.4.3. BSRBR-RA

BSRBR-RA collects baseline data from the recruiting clinician/nurse using a standardized form or directly from each patient enrolled in the registry. Follow-up data are being collected via the hospital, the patient directly, and by linkage with national databases for major health outcomes. The healthcare team at the hospital is contacted every 6 months for the first 3 years and then annually thereafter are asked to complete a standard data form covering any change in treatment over the preceding 6 or 12 months. This includes continuation on drug and dates and reasons for stopping, with details of any change in dose and commencement of any new co-therapy. Clinical information to permit calculation of the DAS28 is also collected.

Registered patients are also contacted every 6 months for the first 3 years and asked to complete a patient diary that includes data about hospital admissions, new hospital referrals, and details of

any new drugs prescribed. They are also asked to complete a series of questionnaires at these time points including the following:

- HAQ
- EQ-5D
- Work Productivity Survey

Following the report of any serious morbidity, either by participant or healthcare professional, the referring doctor is contacted by the BSRBR-RA and asked to provide further details, where available. For specific morbidities of interest, certain specific details are requested. All serious morbidities are coded by a trained nurse using the Medical Dictionary for Regulatory Activities (MedDRA) system, a licensed copy of which is obtained annually.

8.4.4. DANBIO

In DANBIO, data are captured electronically from the source, requiring only little instruction of the patients and health care professionals. DANBIO has developed dedicated touch screens (and from home access) where patients enter data on, for example, disability, pain, lifestyle, and health-related quality of life, in the waiting room or from home. During the consultation, nurses, rheumatologists, and other healthcare professionals add data on, for example, joint counts and medications on their computers.

The validity of the RA diagnosis in DANBIO, is >80%, and has been described elsewhere (Hallager et al., 2017). Registrations of medications (exposure) are prospectively validated at department level as part of the annual quality report. It is estimated, by DANBIO, that the overall error rate is < 5% for the Anatomical Therapeutic Chemical level. For outcomes, these are captured through linkage with national administrative registries, which are virtually complete. The error rate varies between outcomes and is estimated to be <5% at the ICD-10 chapter level and <10% at the 3-digit level.

In addition, DANBIO will link registry patients to national health and demographic registers in Denmark for additional data.

A) The Civil Registration System (CRS) of Denmark

Since 1968, each person residing in Denmark is given a unique identification number, the central person registration (CPR) number, which serves as a key reference to the individual in all public registers (Pedersen, 2011; Pedersen et al., 2006). The CPR number is used to link individual data from the registers.

B) The Danish National Patient Register (DNPR)

The register contains data on all hospital contacts since 1976. The data available today includes inpatient hospitalization, emergency room visits, outpatient hospital visits, admission and discharge dates, all surgical procedures, and all diagnosis codes. The diagnoses are based on international classification of disease, Version 10 (ICD 10 codes).

C) The Danish National Database of Reimbursed Prescriptions

The Danish health care system provides partial reimbursement of almost all prescription medications in Denmark. Since 2004, information on all reimbursed prescriptions has been gathered in the Danish National Database of Reimbursed Prescriptions. Medication administration in hospitals is not registered by CPR numbers, and this information can therefore not be used for individual level analyses. The medicinal products are classified according to the World Health Organization Anatomical Therapeutic Classification System (ATC) coding system (Pottegård et al., 2017; Sørensen et al., 1995; Sørensen & Larsen, 1994).

D) Statistics Denmark

Statistics Denmark (<http://www.dst.dk>) was established in 1850. The institution collects detailed socioeconomic information on all Danish inhabitants regarding education, occupation, economics, etc., has a copy of the national health registers; and makes the data available for research.

E) The Danish National Register of Causes of Death

Since 1875, the National Board of Health has maintained this register of deaths among Danish inhabitants dying in Denmark, and since 1970 the records have been computerized. From 1994, the classification of cause of death was based on ICD 10 codes (Helweg-Larsen, 2011). Data are made available for research by electronical access to a pseudonymized data copy via a safe and password protected data portal at the Danish Health Data Authority (<https://sundhedsdatastyrelsen.dk>), or at Statistics Denmark (above). Besides the public registers, there is a range of clinical databases available for register-based research.

